11.1.4.6 Hypertension

Hypertension is a common class effect of drugs that inhibit VEGF pathways and has been reported in patients treated with cabozantinib.

Blood pressure should be monitored in a constant position at each visit (either sitting or supine). Treatment guidelines for hypertension deemed related to cabozantinib are presented in [Table 11.1-5](#). In general, patients with known hypertension should be optimally managed prior to study entry. Decisions to decrease or hold the dose of study treatment must be based on blood pressure

readings taken by a medical professional and must be confirmed with a second measurement at least 5 minutes following the first measurement. Other than for hypertension requiring immediate therapy, the presence of new or worsened hypertension should be confirmed at a second visit before taking therapeutic action. It is recommended that this second visit occurs within 1 week.

Table 11.1-5: Management of Treatment-emergent Hypertension

Criteria for Dose Modification	Action To Be Taken

> 150 to <160 mm Hg (systolic) OR > 100 to <110 mm Hg (diastolic)
	
 • Optimize antihypertensive treatment by adding new or additional antihypertensive medications and/or increase dose of existing medications. • Reduce cabozantinib treatment by one dose level if optimal antihypertensive therapy (usually to include 3 agents) does not result in BP < 150 mm Hg systolic or < 100 mm Hg diastolic. • If patient is symptomatic interrupt study treatment.

≥ 160 mm Hg (systolic) OR ≥ 110 mm Hg (diastolic)
	
 • Reduce cabozantinib treatment by one dose level and add new or additional antihypertensive medications and/or increase dose of existing medications and monitor patient closely for hypotension. If optimized antihypertensive therapy (usually to include 3 agents) does not result in BP < 150 mm Hg systolic or < 100 mm Hg diastolic, cabozantinib treatment should be dose reduced further or interrupted. • Interrupt cabozantinib treatment if upper limits of BP (≥ 160 mm Hg systolic or ≥ 110 mm Hg diastolic) are sustained and not adequately manageable or if BP is > 180 mm Hg systolic or > 120 mm Hg diastolic or if patient is symptomatic. • Restart cabozantinib treatment at the most tolerable dose and re-escalate cabozantinib dose only if BP falls to and is sustained at < 140 mm Hg systolic and < 90 mm Hg diastolic.

Hypertensive crisis or hypertensive encephalopathy
	
 • Discontinue cabozantinib treatment

BP, blood pressure.

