- a. Unable to receive oral medications or any condition that may prevent adequate absorption of oral study medication including refractory nausea and vomiting, uncontrolled diarrhea, malabsorption, small bowel resection or gastric bypass surgery, use of feeding tubes
- b. Major surgery (e.g., GI surgery) within 6 weeks before first dose of study treatment or incomplete wound healing from any prior surgery. Patients with clinically relevant ongoing complications (per investigator assessment) from prior surgery are not eligible.
- c. The patient has uncontrolled, significant current or recent illness including, but not limited to, the following conditions:
 - Cardiovascular disorders:
 - i. Symptomatic congestive heart failure, unstable angina pectoris, serious cardiac arrhythmias
 - ii. Uncontrolled hypertension defined as sustained BP > 150 mm Hg systolic or > 100 mm Hg diastolic despite optimal antihypertensive treatment

- Stroke (including TIA), myocardial infarction, or other ischemic event within 6 mo before randomization
- Gastrointestinal (GI) disorders including those associated with a high risk of perforation or fistula formation:
 - i. Tumors invading the GI tract, active peptic ulcer disease, inflammatory bowel disease, diverticulitis, cholecystitis, symptomatic cholangitis or appendicitis, acute pancreatitis or acute obstruction of the pancreatic or biliary duct, or gastric outlet obstruction
 - ii. Abdominal fistula, gastrointestinal perforation, bowel obstruction, or intraabdominal abscess within 6 mo before randomization
 - iii. Complete healing of an intra-abdominal abscess must be confirmed before randomization
- Clinically significant hematuria, hematemesis, or hemoptysis of > 0.5 teaspoon (2.5 mL) of red blood, or other history of significant bleeding within 3 mo before randomization
- Moderate to severe hepatic impairment (Child-Pugh B or C)
- Lesions invading major pulmonary blood vessels
- d. Known active infection with HIV or Hepatitis B or C virus
- e. Anticoagulation with warfarin at therapeutic doses is prohibited.
 - Note: Anticoagulation with therapeutic doses of low molecular weight heparin (LMWH), direct thrombin inhibitors, factor Xa inhibitors, and platelet inhibitors (e.g., clopidogrel) is allowed in patients without brain metastases who are on stable doses for at least 4 weeks before randomization and have had no complications from the anticoagulation regimen.

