11.1.3.2 Study Drug Dose Modifications

Dose modifications may be considered for each study drug independently. Modifications, including dose interruption and resumption, dose reduction, dose re-escalation, and permanent

discontinuation of each study drug will be based on the investigator's discretion, with the following exceptions:

- The dose of each study drug cannot exceed the starting dose
- Interruptions of study drug are allowed for up to 6 weeks (continuous) without Medical Monitor consultation, although it is strongly recommended that interruptions in dosing are as brief as possible. Resumption of study drug in a patient with a dose interruption lasting > 6 weeks requires discussion with and approval by the Medical Monitor (see [Section 11.2](#))
- Both study drugs should be interrupted for Grade ≥ 3 elevated ALT, AST, or bilirubin and restarted at reduced doses after ALT, AST, and bilirubin levels resolve to Grade ≤ 1 or baseline
- Suspected drug-induced liver injury should be reported to the Medical Monitor; both study drugs should be interrupted and then resumed only after discussion with and approval by the Medical Monitor (see [Section 11.1.4.2](#))
- Dose re-escalation is not allowed for a dose reduction triggered by study drug-related myelosuppression or Grade 4 life-threatening AEs affecting major organs
- Permanently discontinue cabozantinib for any of the following:
 - Development of unmanageable fistula or GI perforation
 - Severe hemorrhage
 - Arterial thromboembolic event (e.g., myocardial infarction, cerebral infarction)
 - Hypertensive crisis or severe hypertension despite optimal medical management
 - Nephrotic syndrome
 - Reversible posterior leukoencephalopathy syndrome

Additional guidelines for treatment modifications and AE management are provided below in [Table 11.1-3](#) and in [Section 11.1.4](#). These guidelines are based on the Cabometyx (cabozantinib) US Prescribing Information and the clinical experience with CB-839, cabozantinib, and the combination to date. Because cabozantinib prescribing information may change over time, the most up-to-date Cabometyx (cabozantinib) US Prescribing Information (or local equivalent) should also be consulted and followed.

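### Table 11.1-5 tests for failed blood-pressure control with 'or' where 'and' is needed, so a patient with only one pressure uncontrolled falls outside the cabozantinib dose-reduction advice

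*Protocol*

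**What the plan says.** Protocol section 11.1.4.6, Table 11.1-5, sets out the management of treatment-emergent hypertension. Row 1 is entered at systolic pressure above 150 and below 160 mm Hg, or diastolic above 100 and below 110. Row 2 is entered at systolic 160 or more, or diastolic 110 or more. One high pressure is enough for either row.

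- **Row 1:** optimize antihypertensives, then lower cabozantinib by one level if optimal therapy "does not result in BP < 150 mm Hg systolic or < 100 mm Hg diastolic". Its only other cabozantinib action is "If patient is symptomatic interrupt study treatment".
- **Row 2:** the first step is unconditional: "Reduce cabozantinib treatment by one dose level and add new or additional antihypertensive medications". If optimized therapy then fails the same test, in the same words, "cabozantinib treatment should be dose reduced further or interrupted". A separate bullet interrupts cabozantinib if pressures at the row 2 limits "are sustained and not adequately manageable or if BP is > 180 mm Hg systolic or > 120 mm Hg diastolic", or if there are symptoms.
- **Re-escalation, same table:** allowed only if pressure falls to and "is sustained at < 140 mm Hg systolic and < 90 mm Hg diastolic".

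At entry, exclusion criterion 2c (section 8.2) reads "Uncontrolled hypertension defined as sustained BP > 150 mm Hg systolic or > 100 mm Hg diastolic despite optimal antihypertensive treatment".

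**The concern.** A negated 'or' is a strict condition. If therapy fails only when it achieves neither target, then reaching one target counts as success. A patient who enters row 1 at 158/90 already has a diastolic pressure under 100, so the literal test counts control as achieved before any drug is added. That defeats the row for everyone who enters it on a single pressure.

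Both arms receive cabozantinib. Section 11.1.2 lists hypertension among its most frequent adverse events (at least 25% of patients) and among Grade 3-4 reactions seen in at least 5%, and it names hypertensive crisis among the severe, potentially lethal events. In the Phase 1 combination cohort (Table 9.5-2), 2 of 13 patients had treatment-related hypertension, one of them at Grade 3 or higher. What is at stake is whether the table prompts a dose reduction when one pressure stays high.

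**Working it through.** No statistical figure is involved; this is a logic check. Let S and D be the systolic and diastolic pressures on optimal therapy.

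1. **Test as printed:** not (S < 150 or D < 100). By De Morgan's rule this equals S ≥ 150 **and** D ≥ 100.
2. **Test with 'and':** not (S < 150 and D < 100), which equals S ≥ 150 **or** D ≥ 100.
3. **Example pressures, asymptomatic patient:**

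| Pressure on optimal therapy | Row range it falls in | As printed | With 'and' |
|---|---|---|---|
| 158/90 | 1 | not met | met |
| 142/105 | 1 | not met | met |
| 155/104 | 1 | met | met |
| 145/95 | neither | not met | not met |
| 150/90 | neither (settled from a higher reading) | not met | met |
| 140/100 | neither (settled from a higher reading) | not met | met |
| 165/90 | 2 | not met | met |
| 140/112 | 2 | not met | met |

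4. **Whole of row 1.** Take integer pressures with S from 100 to 159 and D from 60 to 109.
   - Points inside row 1: 9 × 50 (S 151-159, any D) + 51 × 9 (S 100-150, D 101-109) = 450 + 459 = 909.
   - The printed test is met at 9 × 10 (S 151-159, D 100-109) + 9 (S = 150, D 101-109) = 99 of them.
   - The remaining 909 − 99 = 810 have exactly one pressure at or above its limit. The printed test is met at 0 of the 810, the corrected test at all 810.
   - These counts illustrate the logic; they are not patient frequencies.
5. **Extent of the gap.** Below the row 2 limits, the two tests differ only for S 150-159 with D < 100, or S < 150 with D 100-109.
6. **Row 2.** A patient who enters at 165/85 and settles at 155/85 gets the first reduction, but the printed test does not trigger the next step. The interruption bullet does not fill that gap without symptoms, because its lowest limits are 160 and 110. A patient who stays at 165/90 or 140/112 can still be caught by that bullet if the pressure is not adequately manageable.
7. **Direction.** S ≥ 150 and D ≥ 100 together imply S ≥ 150 or D ≥ 100, so the printed test is never met where the corrected one is not. The correction only adds recommendations.
8. **Intent.** Under 2c a sustained 158/90 despite optimal treatment is uncontrolled at screening, yet the on-study test read literally treats it as controlled. The re-escalation line asks for both pressures to be low. Row entry needs only one to be high. All three agree with 'and'.

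**The case against.** The best counter-argument is that the phrase is ambiguous rather than plainly wrong. In ordinary English it can be read as failing to bring systolic below its limit, or failing to bring diastolic below its limit, which is the intended rule. Many clinicians would read it that way. This stands as a reason to expect little harm. It does not justify leaving a dosing table in a multicenter trial open to two readings with opposite actions.

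The consequence is also softened by other provisions, and these points stand:

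- Under section 11.1.3.2, modification up to and including permanent "discontinuation of each study drug will be based on the investigator's discretion, with the following exceptions", so a reduction is never barred. One listed exception stops cabozantinib permanently for crisis or for severe hypertension despite optimal management, and it does not use this test.
- The same section makes these guidelines recommendations and tells sites to follow current prescribing information. That information is not in the documents, so it cannot be shown to close the gap.
- The grade-based scheme in Table 11.1-3 may apply, but the documents do not map these pressures to grades.
- Row 1's instruction to optimize antihypertensives applies on either reading. Row 2's first reduction could arguably be applied again to a patient still above the row 2 limits.

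The boundary cases 150/90 and 140/100 are the weakest examples. They are not uncontrolled under 2c, which uses strict inequalities, and rest only on the table's own less-than signs.

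**Conclusion.** The concern holds as a minor patient-safety wording error. Read literally, both rows require both pressures to remain high before control counts as failed. With one pressure uncontrolled in an asymptomatic patient, row 1 gives no explicit advice to reduce cabozantinib, and row 2 gives none under this test beyond its first reduction. The practical gap is mainly one pressure lingering at 150-159 systolic or 100-109 diastolic.

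The conclusion rests on the literal reading. The error withholds a recommendation; it does not forbid a reduction. The number of patients affected is not given. Sample size, type I error, power, endpoints and analyses are untouched.

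**What to change.** In both pressure rows, state the test positively: take the dose step if systolic pressure remains at or above 150 mm Hg **or** diastolic pressure remains at or above 100 mm Hg despite optimal antihypertensive therapy (usually three agents). Changing 'or' to 'and' in the existing phrase is logically equivalent, but the positive form avoids the negation that causes the trouble.

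The edit is one word or one clause in each of two rows, with no effect on sample size, analysis or schedule. Section 18.0 requires sponsor and IRB/IEC approval for protocol changes, so there is a small administrative cost. Attachment 9 shows that a typographical error in inclusion criterion 3e was handled by a clarification letter to sites and ethics bodies before the amendment; the same route would serve here. SAP section 4.2 describes enrollment in the past tense, so the benefit is to patients still on treatment.

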11.1.4.7 Thromboembolic Events

Thromboembolic complications are frequent in cancer patients due to procoagulant changes induced by the malignancy or anti-cancer therapy including inhibitors of VEGF pathways. Deep vein thrombosis and PE have been observed in clinical studies with cabozantinib; including fatal

events. Patients who develop a PE or DVT should have cabozantinib treatment held until therapeutic anticoagulation with heparins (e.g., LMWH) is established. (Note: Initiation of therapeutic anticoagulation is allowed on study in consultation with the Sponsor's medical monitor.) Cabozantinib treatment may be resumed in patients who are stable and have uncomplicated PE or DVT and are deriving clinical benefit from cabozantinib treatment. During anticoagulation treatment, patients need to be monitored on an ongoing basis for bleeding risk and signs of bleeding which may require additional or more frequent laboratory tests according to institutional guidelines. If there are any signs of clinically relevant bleedings, cabozantinib treatment should be interrupted immediately and the sponsor contacted to discuss further study participation. Patients with life-threatening PE or DVT should have study treatment discontinued unless toxicity can be managed and patient is deriving clear clinical benefit as determined by the investigator and agreed by the Sponsor.

Arterial thrombotic events (e.g., transient ischemic attack, myocardial infarction) have been observed rarely in studies with cabozantinib. Patients should be evaluated for preexisting risk factors for arterial thrombotic events such as diabetes mellitus, hyperlipidemia, hypertension, coronary artery disease, history of tobacco use, and cardiac or thromboembolic events that occurred prior to initiation of study treatment. Cabozantinib treatment should be discontinued in patients who develop an acute myocardial infarction or any other clinically relevant arterial thromboembolic complication.

11.1.4.8 Proteinuria

Proteinuria is an anticipated AE with the inhibition of VEGF pathways and has been observed in cabozantinib clinical studies, and nephrotic syndrome has been reported with cabozantinib and other inhibitors of VEGF pathways. Urine protein should be monitored regularly during cabozantinib treatment. Guidelines for proteinuria management are described in [Table 11.1-6](#). Cabozantinib should be discontinued in patients who develop nephrotic syndrome.

Table 11.1-6: Management of Treatment-emergent Proteinuria

Severity of Proteinuria (UPCR)	Action To Be Taken
≤ 1 mg/mg (≤ 113.1 mg/mmol)	No change in cabozantinib treatment or monitoring
> 1 to < 3.5 mg/mg (> 113.1 to < 395.9 mg/mmol)	
 No change in cabozantinib treatment required Consider confirming with a 24-hour protein assessment within 7 days Repeat UPCR within 7 days and once per week. If UPCR < 1 on 2 consecutive readings, UPCR monitoring can revert to protocol-specific times. (Second reading is confirmatory and can be done within 1 week of first reading.)
≥ 3.5 mg/mg (≥ 395.9 mg/mmol)	
 Hold cabozantinib treatment pending repeat UPCR within 7 days and/or 24-hour urine protein. If ≥ 3.5 on repeat UPCR, continue to hold cabozantinib treatment and check UPCR every 7 days. If UPCR decreases to < 2, restart cabozantinib treatment at a reduced dose and monitoring of urine protein/creatinine should continue weekly until the UPCR decreases to < 1.
Nephrotic syndrome	Discontinue cabozantinib treatment

UPCR, urine protein to creatinine ratio.

11.1.4.9 Hypophosphatemia

Hypophosphatemia has been reported during treatment with cabozantinib. Serum phosphorus should be monitored frequently while receiving cabozantinib. Mild hypophosphatemia is usually asymptomatic or symptoms can be non-specific such as weakness, bone pain, rhabdomyolysis, or altered mental status. Other causes of hypophosphatemia such as poor nutrition, chronic alcoholism, malabsorption, excessive antacid use, glucocorticoids use, kidney dysfunction, respiratory alkalosis, vitamin D deficiency should be ruled out and/or these causes treated according to standard of care. Mild to moderate hypophosphatemia should be managed by oral replacement including food that are high in phosphate (diary items, meats, beans) and/or oral phosphate supplements according to standard clinical practice guidelines. Clinically relevant hypophosphatemia should be managed according to the dose modification guidelines as outlined in [Table 11.1-3](#) or as clinically indicated.

11.1.4.10 Thyroid Function Disorders

Changes in thyroid function tests (TFTs) and hypothyroidism have been reported with cabozantinib and other tyrosine kinase inhibitor treatment as a result of altered thyroid hormone

regulation by mechanisms that seem to be specific for each agent ([Torino 2009](#)). Preliminary data from ongoing studies indicate that treatment-emergent elevation of thyroid stimulating hormone (TSH) by cabozantinib may be dose-dependent in fashion. Currently available data are insufficient to determine the mechanism of TFT alterations and its clinical relevance. Monitor thyroid function as outlined in [Attachment 1](#). Management of thyroid dysfunction (e.g., symptomatic hypothyroidism) should follow accepted clinical practice guidelines.

11.1.4.11 Hemorrhagic Events

Hemorrhagic events have been reported with approved drugs that inhibit VEGF pathways as well as with cabozantinib. In order to mitigate risk of severe hemorrhage, patients should be evaluated for potential bleeding risk factors prior to initiating cabozantinib treatment and monitored for bleeding events with serial complete blood counts and physical examination while on study. Risk factors for hemorrhagic events may include (but may not be limited to) the following:

- Tumor of the lung with cavitory lesions or tumor lesions which invades, encases, or abuts major blood vessels. The anatomic location and characteristics of tumor as well as the medical history must be carefully reviewed in the selection of patients for treatment with cabozantinib.
- Recent or concurrent radiation to the thoracic cavity
- Active peptic ulcer disease, ulcerative colitis, and other inflammatory GI diseases
- Underlying medical conditions which affect normal hemostasis (e.g., deficiencies in clotting factors and/or platelet function, or thrombocytopenia)
- Concomitant medication with anticoagulants or other drugs which affect normal hemostasis
- History of clinically significant hemoptysis

Discontinue cabozantinib treatment in patients who have been diagnosed with a severe bleeding complication.

11.1.4.12 GI Perforation/Fistula and Non-GI Fistula Formation

GI perforation/fistula and non-GI fistula formation have been reported with approved drugs that inhibit VEGF pathways as well as with cabozantinib. Carefully monitor for episodes of

abdominal pain, especially in patients with known risk factors for developing GI perforation/fistula or non-GI fistula, to allow for early diagnosis. Such risk factors include (but may not be limited to) the following:

GI perforation/fistula:

- Intra-abdominal tumor/metastases invading GI mucosa
- Active peptic ulcer disease, inflammatory bowel disease, diverticulitis, cholecystitis or symptomatic cholangitis, or appendicitis
- History of abdominal fistula, GI perforation, bowel obstruction, or intra-abdominal abscess
- Prior GI surgery (particularly when associated with delayed or incomplete healing).
Complete healing following abdominal surgery or resolution of intra-abdominal abscess must be confirmed prior to initiating treatment with cabozantinib.

Additional risk factors include concurrent chronic use of steroid treatment or nonsteroidal anti-inflammatory drugs. Constipation indicative of bowel obstruction should be monitored and effectively managed.

Non-GI fistula:

Complications from radiation therapy has been identified as a possible predisposing risk factor for non-GI fistula formation in patients undergoing treatment with VEGF pathway inhibitors (e.g., bevacizumab). Discontinue cabozantinib treatment in patients who have been diagnosed with GI or non-GI perforation/fistula.

11.1.4.13 Osteonecrosis of the Jaw

Osteonecrosis of the jaw (ONJ) has been reported with use of anti-angiogenic drugs and bisphosphonates and denosumab in cancer patients. Additional risk factors for ONJ have been identified such as use of corticosteroids, chemotherapy, local radiotherapy, poor oral hygiene, smoking, dental or orofacial surgery procedures, and cancer disease itself. Osteonecrosis has been reported in patients treated with cabozantinib. As a preventive measure, invasive dental procedures should be avoided if possible in patients who have previously been treated with or concomitantly receive bisphosphonates or denosumab.

In cases where dental procedures are unavoidable, the risks and benefits of a dental procedure and the extent of the procedure as well as the risk of developing osteonecrosis of the jaw need to be considered when deciding on the duration of a temporary treatment interruption of cabozantinib. If clinically possible, treatment with cabozantinib should be held for approximately 4 weeks prior to a dental procedure and resumed after complete healing has occurred.

Patients with any documented case of osteonecrosis should have study treatment interrupted, and appropriate clinical management should be initiated. Reinitiation of study treatment must be discussed with and approved by the Sponsor on a case-by-case basis.

